## **1.0 Introduction**

The purpose of this document is to provide guidelines regarding study procedures for the Impact of Augmented Care at the Worksite for Diabetes Prevention trial. This trial is a single-site clinical trial. Funding for the trial is provided by the National Institute for Diabetes and Digestive and Kidney Diseases at the National Institutes of Health. Since the trial is funded by the federal government, we are responsible for following federal guidelines and completing federal reports.

## **2.0 Brief Overview of the Study Protocol**

The purpose of this study is to implement and evaluate a lifestyle intervention for Ohio State University (OSU) employees with prediabetes to determine the impact of the intervention on weight loss and related outcomes to reduce risk for type 2 diabetes mellitus (T2DM). People with prediabetes are at high risk for progressing to T2DM, and weight loss is the most effective treatment for risk reduction. This study trial follows a preliminary trial to evaluate the efficacy of a lifestyle intervention implemented at a university worksite. The efficacy trial was highly successful in promoting weight loss on average among participants randomized to the experimental group. However, about 50% of experimental participants did not achieve clinically meaningful weight loss. More effective treatments are needed for people who are slower to respond to behavioral interventions. A goal of this trial is to determine whether augmented care for slow responders promotes greater weight loss and risk reduction. Effective weight loss maintenance interventions also are needed to reduce risk for T2DM. We will examine the impact of an extended intervention phase on weight loss maintenance following an intensive lifestyle intervention.

The specific aims of this translational study at a university worksite are to:

**Specific Aim 1:** Implement the first 4-sessions of the core 16-session phase of the Group Lifestyle Balance (GLB) intervention for diabetes prevention to all study participants. GLB is the group-based version of the intervention implemented in the Diabetes Prevention Program. Determine percent weight change at week 5. Provide a 12-session augmented intervention (called Group Lifestyle Balance Plus (GLB+)) to participants who fail to achieve > 2.5% weight loss at week 5; provide the remainder of the 12-session standard GLB intervention to all other participants. GLB+ will be enhanced with training in values clarification, mindful decision making, planning, and problem solving. Evaluate the impact of the augmented GLB+ intervention to the standard GLB intervention immediately following the core intervention phase (4 months from baseline).

**Specific Aim 2:** Create matched pairs of participants based on sex and percent weight change at 4-months following the core intervention phase. Randomly assign each person in the pair to either the standard GLB intervention or to the augmented GLB+ intervention for the 8-month extended intervention phase. Evaluate the impact of the GLB+/GLB+ intervention sequence to the GLB/GLB intervention sequence at 12- and 18-month follow-up. One exploratory sub-aim will be to identify optimal treatment sequences embedded in the adaptive design on percent weight change at 18 months.

**Specific Aim 3:** Estimate the costs and cost-effectiveness of each intervention from a health system and societal perspective.

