### **4.0 Study Flow Diagram**

An overview of the general study processes is provided in Figure 1. In this trial, participants are not randomized to treatment group at baseline. Instead, all participants receive the first four weeks of the standard GLB intervention. During these first four weeks, participants learn basic skills such as self-monitoring, the calorie and fat content of food and beverages, and how to initiate a physical activity program such as brisk walking. Participants then remain in the standard GLB intervention if they achieve at least 2.5% weight loss at week 5. If participants do not achieve this level of weight loss, they will be stratified to the augmented GLB+ intervention at week 5. Participants will be randomized to treatment group following the core intervention phase (first 16 weeks) for the extended (8 months) and maintenance (6 months) intervention phases.

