## **7.0 Research Design and Study Intervention**

Following baseline data collection, all participants will begin the 16-session core phase of the Group Lifestyle Balance (GLB) intervention. Percent weight change will be determined at the beginning of week 5, after 1 month of intervention. Those who achieve  $> 2.5\%$  weight loss will complete the remainder of the 12 GLB sessions. Those who achieve  $\leq 2.5\%$  weight loss will be stratified to the Group Lifestyle Balance Plus (GLB+) intervention (additional 12 sessions). A second round of data collection will

occur upon completion of the core intervention study phase, 4 months from baseline. Following this second data collection, participants will be matched into pairs based on gender and percent weight change at 4 months, and each person in a matched pair will be randomly assigned to treatment group for the extended intervention study phase. One person in each pair will receive either the standard GLB intervention or the augmented GLB+ intervention, and the second person in each pair will receive the alternate intervention. Following completion of the extended intervention study phase at 12 months, a third round of data collection will occur. A 6-month no contact phase will follow the extended intervention study phase to evaluate weight loss maintenance. The fourth and final round of data collection will occur upon completion of the 6-month no contact phase, 18 months from baseline.

The goals of both the GLB and GLB+ interventions include losing  $\geq 7\%$  of initial body weight and maintaining  $\geq 7\%$  weight loss through study end. The intervention group sessions will consist of 10-15 participants (to foster

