## **8.0 Randomization**

Participants will be randomly assigned to treatment group following the 16-week core intervention phase. Participants will be matched, based on gender and percent weight change following the 4-month data collection visit. Each person in a matched pair will be randomly assigned to either the GLB or the GLB+ intervention for the extended and maintenance intervention phases. The biostatistician will create the randomization log and will be blinded to treatment group during the core intervention phase.

- **Process Responsibilities:** The Study Coordinator will maintain the master randomization list from the statistician. The Study Coordinator will be responsible for assigning randomization codes, notifying appropriate study staff that the participant has been randomized, and securely storing all randomization files.

The assigned and blinded randomization code, that is separate from study data, will be kept in a paper-based randomization log in a locked filing cabinet.

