#### ***15.2 Specific Aim 1 Analysis***

It is hypothesized that there will be no significant difference in percent weight change at four months between treatment groups due to the enhanced training provided to early non-responders. A test of equivalence of the two treatments with percent weight change as the response variable will be performed. A stepwise regression model with

Bayes Information Criterion for choosing the final model will be built. Final test of equivalence will be carried out at level of significance 0.05.

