#### ***15.4. Analyses for Comparing Treatment Sequence on Weight Loss Maintenance (sub-aim)***

The analysis for this exploratory sub-aim will compare the 4 treatment sequences embedded in the adaptive design on percent weight change at 18-months. The primary comparison of interest is the GLB/GLB

intervention sequence to the GLB+/GLB+ intervention sequence across the 18-month timeframe. Whether the GLB+ intervention during the extended intervention phase is optimal following the core phase, especially for early non-responders, and whether the GLB+ intervention during the extended intervention phase is necessary to promote weight loss maintenance for those who initially achieved the 2.5% weight loss will be determined. The analysis will be based on an analysis of covariance model, using appropriate covariates (e.g., baseline weight), where we will compare the four groups using an F-test and then perform multiple comparisons using Tukey's HSD test.

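### Specific Aim 2 and the sub-aim name GLB+/GLB+ versus GLB/GLB, which sets early non-responders against early responders and is not the randomised contrast of section 15.3

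*Combined protocol and SAP*

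**What the plan says.** Specific Aim 2 in section 2.0 states its evaluation as follows: "Evaluate the impact of the GLB+/GLB+ intervention sequence to the GLB/GLB intervention sequence at 12- and 18-month follow-up". The exploratory sub-aim (the last part of section 15, headed as comparing treatment sequences) repeats it: "The primary comparison of interest is the GLB/GLB" sequence against the GLB+/GLB+ sequence. Its model is an analysis of covariance "using appropriate covariates (e.g., baseline weight" being the only example), with an F-test over four groups and then Tukey's HSD.

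Two other parts of the plan fix who can be in each sequence:

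- **Core phase.** Treatment follows week-5 response. Section 4.0 says: "If participants do not achieve this level of weight loss, they will be stratified to the augmented GLB+ intervention at week 5". Sections 2.0 and 7.0 give the same rule, apart from how they treat a loss of exactly 2.5%, which does not matter here.
- **Extended phase.** Section 8.0 says: "Participants will be randomly assigned to treatment group following the 16-week core intervention phase". It adds: "Participants will be matched, based on gender and percent weight change following the 4-month data collection visit". Core treatment is not a matching factor.

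The table at the end of section 15.4.2 labels the sequences A (GLB/GLB), B (GLB/GLB+), C (GLB+/GLB) and D (GLB+/GLB+).

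Section 15.3, the Aim 2 analysis, uses a different contrast. It compares participants randomised to GLB+ (expected to keep off at least 7%) with those randomised to GLB (expected 5%), with no split by core treatment. The cost-effectiveness ratio in section 15.4 also compares extended GLB+ with extended GLB.

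**The concern.** No participant could have been randomised between A and D. A person who passes the week-5 cut can reach only A or B, and a person who misses it only C or D. A comparison of D with A therefore carries whatever separates early responders from early non-responders, together with any effect of core GLB+, on top of the extended-phase effect that was randomised.

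The plan also gives one aim two different estimands: D against A in section 2.0, and B and D together against A and C together in section 15.3. Nothing says which is the Aim 2 result. A report that follows the wording of the aim would present a partly non-randomised difference as the effect of the intervention. The sub-aim's conclusion about optimal sequences would rest on the same contrast.

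**Working it through.** The plan states no sample size, SD or power for this comparison, so there is no figure to reproduce. The structural argument comes first, then an illustration of size.

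**1. Decomposition.** Write each letter for the mean 18-month percent weight loss in that sequence. Then

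D − A = (D − C) + (C − A).

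D − C is randomised, among early non-responders. C − A is not randomised: both groups receive extended GLB, but C missed the week-5 cut and had core GLB+, while A passed it and had core GLB. C − A is thus early-response prognosis plus any core GLB+ effect. Section 15.2 expects such an effect, since it predicts no 4-month difference "due to the enhanced training provided to early non-responders".

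**2. Covariates and matching do not repair it.** Within A and D, week-5 response status and core treatment coincide completely. No covariate set can separate them without extrapolating across the cut. Pairs are formed on sex and 4-month change, not on core group, and A against D is not a within-pair comparison.

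**3. Illustrative size, closed form.** Assumed, not from the documents: week-5 and 18-month loss are bivariate normal with correlation r; SD is the 18-month SD; p is the share of non-responders; c is the core GLB+ benefit remaining at 18 months. With no extended-phase effect,

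D − A = c − r × SD × φ(z_p) / (p(1 − p)).

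At p = 0.5 the factor is 0.399/0.25 = 1.596; at p = 0.3 or 0.7 it is 1.656. With p = 0.5 and c = 0:

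- SD 5, r 0.2: −1.596 × 1.0 = −1.60
- SD 7, r 0.3: −1.596 × 2.1 = −3.35
- SD 8, r 0.5: −1.596 × 4.0 = −6.38

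Each point of c moves these up by one point. A true extended-phase effect of +2 (7% − 5%, section 15.3) moves them up by two. Negative values are against GLB+.

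| c | D − A, no extended-phase effect | D − A, true effect +2 |
|---|---|---|
| 0 | −1.6 to −6.4 | +0.4 to −4.4 |
| 1 | −0.6 to −5.4 | +1.4 to −3.4 |
| 2 | +0.4 to −4.4 | +2.4 to −2.4 |
| 3 | +1.4 to −3.4 | +3.4 to −1.4 |

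The distortion vanishes only at c = 1.60, 3.35 or 6.38 in the three cases above, so even its sign depends on an unknown.

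**4. Early response acting only through 4-month change.** This is a simulation with 2 million people per scenario. Assumed: SD 5 at 4 months and 7 at 18 months; week-5/4-month correlation 0.3, 0.5 or 0.7; 4/18-month correlation 0.5 or 0.7; individual 1:1 extended-phase assignment; true effect +2.

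| Share of the 4-month gap closed by core GLB+ | C − A | Apparent D − A for a true +2 |
|---|---|---|
| 0% | −1.68 to −5.48 | +0.32 to −3.48 |
| 50% | −0.86 to −2.73 | +1.15 to −0.74 |
| 100% | −0.02 to +0.02 | 1.98 to 2.02 |

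In all 18 scenarios the randomised contrasts B − A and D − C returned 1.97 to 2.05.

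**5. Matched-pair simulation.** Assumed: 200 people; week-5 loss mean 2.5%, SD 1.5; 4-month SD 4; week-5/4-month correlation 0.3 to 0.7; 0.8 carried forward to 18 months; core GLB+ effect 0 or 2 points; pairs matched on sex and 4-month loss. For a true effect of 2, the section 15.3 contrast gave 1.95 to 2.02, while D − A gave −1.61 to +2.06. For a true effect of 0, the section 15.3 contrast gave −0.02 to +0.02, while D − A gave −3.60 to +0.12. Only 50% to 66% of pairs had both members from the same core group.

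**The case against.** The strongest reply is that the operative analysis is already sound. The aim is one sentence in an overview, whereas section 15.3 compares randomised arms using the matched pairs, and an analyst working from section 15 would not run D against A for Aim 2. The only analysis that names that pair is exploratory. It also asks about extended GLB+ for early non-responders (D − C) and for those who met the cut (B − A), and Tukey's HSD yields both. This stands as a limit on severity. It does not remove the conflict between the aim and its analysis, or the sub-aim's choice of the confounded pair as primary.

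D against A could also be read descriptively, as asking whether slow responders given augmented care catch up. That is a reasonable question, but the aim speaks of impact, which is causal language, and the plan nowhere labels the comparison descriptive.

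A strict week-5 cut would in principle allow a regression-discontinuity estimate near the threshold. No such analysis is planned, and it would give only a local effect, not the sequence comparison named.

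Finally, every input to the size calculation is assumed. Under section 15.2's own hypothesis, with early response acting only through 4-month change, the distortion is about zero. That is correct, but it makes the Aim 2 estimate depend on a hypothesis the trial is itself testing, and at 18 months rather than 4. The structural argument does not depend on the figures.

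**Conclusion.** The concern holds and should be fixed. As worded, Specific Aim 2 and the sub-aim's primary comparison set early non-responders against early responders, and they disagree with the randomised contrast in section 15.3 and in the cost-effectiveness ratio. This follows from the allocation rules alone.

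The size and direction of the distortion cannot be determined from the documents. Over the closed-form range with c from 0 to 3, a true 2-point benefit could appear as anything from +3.4 to −4.4 points, so the contrast could hide, reverse or overstate a benefit. The section 15.3 analysis is not affected. The risk is to what is reported under Aim 2 if the aim's wording is followed, and to the sub-aim's conclusion about sequences.

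**What to change.** 1. Reword Specific Aim 2 to match section 15.3, for example: *Evaluate the effect of GLB+ compared with GLB in the extended phase, among all randomised participants, on percent weight change at 12 and 18 months.*
2. In the sub-aim, make B − A (early responders) and D − C (early non-responders) the main comparisons. Estimate both from one model with extended-phase arm, core stratum and their interaction, adjusted for sex and 4-month percent weight change, and keep them exploratory.
3. Label A against D, and the other pairs that cross core strata (A–C, B–C, B–D), descriptive and non-randomised.
4. State whether the four-group F-test and Tukey's HSD remain, how multiplicity is handled for the two named contrasts, and how pairs that span core strata enter the model.

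The cost is a small change to the sub-aim model and some wording, with no new data or visits. The precision of the two within-stratum contrasts has not been assessed, because the documents give no sample size or SD. The trial gives up a causal claim about GLB+/GLB+ against GLB/GLB, which the planned analysis cannot support.

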### **3.0 Study Staff Responsibilities**

[figure not shown]
In this single-site study, the site staff perform the following functions:

- Develop all study materials including the Procedures Manual and study forms
- Monitor for and report Adverse Events and Serious Adverse Events
- Obtain informed consent from each participant
- Recruit, screen, and enroll participants
- Randomize participants
- Collect study data and follow participants through study completion
- Comply with study intervention administration
- Protect participants' rights
- Submit documents to regulatory bodies (i.e., IRB, Safety Officer, NIDDK)
- Develop and implement:
  - Data management procedures including the data flow and procedures for data entry, error identification, and correction
  - Quality control procedures
  - Reports - enrollment, participant status (e.g., withdrawals), adverse events, and independent safety monitoring body reports

### **4.0 Study Flow Diagram**

An overview of the general study processes is provided in Figure 1. In this trial, participants are not randomized to treatment group at baseline. Instead, all participants receive the first four weeks of the standard GLB intervention. During these first four weeks, participants learn basic skills such as self-monitoring, the calorie and fat content of food and beverages, and how to initiate a physical activity program such as brisk walking. Participants then remain in the standard GLB intervention if they achieve at least 2.5% weight loss at week 5. If participants do not achieve this level of weight loss, they will be stratified to the augmented GLB+ intervention at week 5. Participants will be randomized to treatment group following the core intervention phase (first 16 weeks) for the extended (8 months) and maintenance (6 months) intervention phases.

**Figure 1: Study Flow Diagram**

## 5.0 Recruitment and Retention

A wide variety of recruitment strategies will be used to attract and enroll a sufficient number of participants into the study. A general description of avenues for recruitment and tips for professional engagement are included in the Recruitment Guidelines. Only IRB approved recruitment material can be used. Any changes or additions to recruitment material must be reviewed and approved by the IRB prior to using.

It is vital to not only recruit participants but also retain participants in the study until the final data collection visit, 18 months from baseline. To promote retention, the following procedures will be used:

- Mail birthday cards to participants during their birthday month;
- Mail holiday cards to participants during key holidays (exclusive of religious holidays)
- Provide contact information to participants for the PI, Study Coordinator, and Lifestyle Coach

- Contact participants in the manner they prefer; use e-mail or phone messages based on the participant's preferred method of communication
- Schedule clinic visits and study appointments at a convenient time for the participant
- Reschedule missed appointments as soon as possible
- Provide a parking voucher for participants for study visits who do not have a valid OSU parking permit
- Provide a modest honorarium for completing data collection visits

Use blue ink when signing greeting cards. Use professional language and sentiments in all communications. Letters and other correspondence should be placed on study letterhead.

### **5.1 Screening and Eligibility Criteria**

OSU is among the largest public universities in the U.S. and employs ~44,000 individuals. Recruitment will include advertisements on the daily electronic news service sent to all OSU employees, notices on campus web sites, information about the study at employee biometric screenings, and through university flyers placed throughout campus. In addition, an email message regarding the study and eligibility criteria will be sent to all university employees. A telephone number and e-mail address will be provided for employees to contact for more information. Those who inquire about the study will receive a description of the study and time commitment and, if interested, complete a telephone screening questionnaire to assess potential study eligibility after providing verbal consent. All potentially eligible employees will be scheduled for an individual appointment to obtain informed consent, complete weight and glucose screenings, and complete the Physical Activity Readiness Questionnaire, Patient Health Questionnaire-8, and Binge Eating Scale (see exclusion criteria). Eligible enrollees then will complete baseline data collection, which includes completion of study questionnaires, a food frequency questionnaire, 7-day assessment of physical activity, and assessment of blood lipids and blood pressure.

### **5.2 Screening Log**

The Screening, Enrollment, and Randomization Log will provide documentation of all individuals evaluated for study eligibility. Enter codes documenting the reason for individuals who are ineligible or eligible but decline study participation.

### **5.3 Eligibility Criteria**

#### **5.3.a Inclusion Criteria**

The eligibility criteria target a sample at risk for diabetes representative of working adults. Both men and women  $\geq 21$  years old from all racial/ethnic groups will be eligible. Benefits-eligible employees will need to be employed by OSU through the length of follow-up and commit to attend treatment and assessment appointments. The inclusion criteria represent benefit-eligible employees at OSU, which is appropriate for a working population.

In addition to the above criteria, the goal of the study is to recruit participants with prediabetes. OSU employees are encouraged to complete an annual biometric screening, which includes an A1c assessment. A fasting glucose and A1c measurement will be used in this study to predict risk for impaired glucose tolerance. Height and weight measurement and a blood sample by finger stick will be completed to assess casual capillary blood glucose (CCBG) concentration and A1c for people with a BMI  $> 24 \text{ kg/m}^2$  ( $> 21 \text{ kg/m}^2$  for Asians). People with a CCBG  $\geq 200 \text{ mg/dL}$  will be ineligible and informed that they are at high risk for diabetes and should see their physician to undergo formal testing and follow-up. Individuals with a fasting CCBG of 100-125 mg/dL (110-199 mg/dL if non-fasting in previous 2 hr.) will be potentially eligible. Those with an A1c value of 5.7-6.4% will be potentially eligible. These individuals will be assessed for any exclusionary criteria to determine final study eligibility.

